- _____(Y) 1. Does the patient have pathologically (histologically or cytologically) proven diagnosis (from primary lesion and/or lymph nodes) of squamous cell carcinoma of the oropharynx, hypopharynx, or larynx? (**Note:** Patients with oral cavity, nasopharynx, sinuses and salivary gland primary tumors are excluded.)
- _____(Y/N) 2. Does this patient have oropharynx primary? If yes, the patient must agree to consent for mandatory submission of tissue required for central review.
- _____(Y) 3. Does the patient have selected stage III or IV disease: any anatomic site T2 N2-3 M0, T3-4 any N M0; p16 negative oropharynx cancer with T1 N2b, N2c, or N3; or hypopharynx T1-2 any N+?
- _____(Y) 4. Was a history and physical examination done within 28 calendar days prior to registration, including assessment of patient's weight?
- _____(Y) 5. Was the patient examined by a Medical Oncologist and a Radiation Oncologist within 28 calendar days prior to registration?
- _____(Y) 6. Was the patient examined by an ENT or Head and Neck Surgeon (including laryngopharyngoscopy) within 42 days prior to registration?
- _____(Y) 7. Was a Chest CT scan or PET/CT done within 42 calendar days prior to registration ?
- _____(Y) 8. Was a contrast enhanced CT scan or MRI or PET/CT scan of the tumor site and neck nodes done within 42 calendar days prior to registration?
- _____(N) 9. Does the patient have distant metastases?
- _____(Y) 10. Was an EKG and ECHO or MUGA scan done within 84 calendar days prior to registration?
- _____(Y) 11. Was the Zubrod Performance Status 0-1 within 14 calendar days prior to registration?
- _____(Y) 12. Is the patient \geq 18 years of age?
- _____(Y) 13. Does the patient have adequate bone marrow, hepatic and renal function as specified in Section 3.1?
- _____(Y) 14. Were magnesium, calcium, glucose, potassium and sodium done within 14 calendar days prior to registration with results within the parameters required in Section 3.1?
- _____(Y/NA) 15. For women of child bearing potential, was a serum pregnancy test completed within 14 calendar days prior to registration?
- _____(Y) If yes, was the pregnancy test negative?
- _____(Y/NA) 16. If the patient is a woman of child bearing potential or a sexually active male, is the patient willing to use effective contraception during treatment and for at least 60 calendar days following the last study treatment?
- _____(Y) 17. Will the patient be compliant with treatment plan and follow-up schedule?

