3.1 Conditions for Patient Eligibility (9/27/16)

3.1.1 Pathologically (histologically or cytologically) proven diagnosis (from primary lesion and/or lymph nodes) diagnosis of squamous cell carcinoma of the oropharynx, hypopharynx, or larynx;

3.1.2 For patients with an oropharynx primary, the tumor must be negative for p16 by immunohistochemistry;

3.1.3 Selected stage III or IV disease: patients with T2 N2-3 M0, T3-4 any N M0 are eligible; in addition, p16 negative oropharynx cancer T1 N2b, N2c, or N3; and hypopharynx cancer patients with T1-2 any N+ are eligible, including no distant metastases, based upon the following minimum diagnostic workup:

3.1.3.1 History/physical examination within 28 calendar days prior to registration, including an examination by a Medical Oncologist and Radiation Oncologist and documentation of the patient's weight;

3.1.3.2 Examination by an ENT or Head & Neck Surgeon, including laryngopharyngoscopy (mirror and/or fiberoptic and/or direct procedure) within 42 days prior to registration;

3.1.3.3 Chest CT scan, or PET/CT scan within 42 calendar days prior to registration to rule out metastatic disease;

3.1.3.4 Contrast enhanced CT scan or MRI or PET/CT scan of the tumor site and neck nodes within 42 calendar days prior to registration;

3.1.3.5 EKG and ECHO or MUGA scan within 84 calendar days prior to registration;

- 3.1.4 Zubrod Performance Status 0-1 within 14 calendar days prior to registration;
- 3.1.5 Age \geq 18;
- 3.1.6 CBC/differential obtained within 14 calendar days prior to registration, with adequate bone marrow function defined as follows:
 - 3.1.6.1 Absolute neutrophil count (ANC) \geq 1,500 cells/mm³;
 - 3.1.6.2 Platelets \geq 100,000 cells/mm³;
 - 3.1.6.3 Hemoglobin \geq 8.0 g/dl (Note: The use of transfusion or other intervention to achieve Hgb \geq 8.0 g/dl is acceptable.);
- 3.1.7 Adequate renal and hepatic function within 14 calendar days prior to registration, defined as follows:
 - 3.1.7.1 Serum creatinine < 1.5 mg/dl or creatinine clearance (CC) \geq 50 ml/min within 14 calendar days prior to registration, determined by 24-hour collection or estimated by Cockcroft-Gault formula:
 - CCr male = [(140 – age) x (wt in kg)]
[(Serum Cr mg/dl) x (72)]
 - CCr female = 0.85 x (CrCl male)
 - 3.1.7.2 Total bilirubin < 2 x the institutional ULN;
 - 3.1.7.3 AST or ALT \leq 3 x the institutional ULN;

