- 3.1.8 Magnesium, calcium, glucose, potassium, and sodium within 14 calendar days prior to registration, with the following required parameters:
 - 3.1.8.1 Magnesium: > 0.9 mg/dl or < 3 mg/dl;
 - 3.1.8.2 Calcium: > 7 mg/dl or < 12.5 mg/dl;
 - 3.1.8.3 Glucose: > 40 mg/dl or < 250 mg/dl;
 - 3.1.8.4 Potassium: > 3 mmol/L or < 6 mmol/L;
 - 3.1.8.5 Sodium: > 130 mmol/L or < 155 mmol/L.
- 3.1.9 Negative serum pregnancy test within 14 calendar days prior to registration for women of childbearing potential;
- 3.1.10 Women of childbearing potential and men who are sexually active must practice adequate contraception during treatment and for at least 60 calendar days following treatment.
- 3.1.11 Patients must be deemed able to comply with the treatment plan and follow-up schedule.
- 3.1.12 Patients must provide study specific informed consent prior to study entry, including, for oropharyngeal cancer patients, consent for mandatory submission of tissue for required, central p16 review.

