- 3.2.13.5 Chronic Obstructive Pulmonary Disease exacerbation or other respiratory illness requiring hospitalization or precluding study therapy within 30 calendar days prior to registration;
- 3.2.13.6 Hepatic insufficiency resulting in clinical jaundice and/or coagulation defects; note, however, that laboratory tests for liver function and coagulation parameters are not required for entry into this protocol.
- 3.2.13.7 Acquired Immune Deficiency Syndrome (AIDS) based upon current CDC definition; note, however, that HIV testing is not required for entry into this protocol. The need to exclude patients with AIDS from this protocol is necessary because the treatments involved in this protocol may be significantly immunosuppressive. Protocol-specific requirements may also exclude immuno-compromised patients.

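### As drafted, the five electrolyte and glucose entry limits in Section 3.1.8 exclude no value, and the liver-test entry wording needs reconciling

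*Combined protocol and SAP*

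**What the plan says.** **Electrolytes and glucose.** Section 3.1.8 asks for five tests within 14 calendar days before registration and presents their limits as required:

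- "Magnesium: > 0.9 mg/dl or < 3 mg/dl" (3.1.8.1)
- "Calcium: > 7 mg/dl or < 12.5 mg/dl" (3.1.8.2)
- "Glucose: > 40 mg/dl or < 250 mg/dl" (3.1.8.3)
- "Potassium: > 3 mmol/L or < 6 mmol/L" (3.1.8.4)
- "Sodium: > 130 mmol/L or < 155 mmol/L" (3.1.8.5)

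Item 14 of the Step 1 Eligibility Checklist asks whether these tests were done "prior to registration with results within the parameters required in Section 3.1". It gives no ranges of its own. The study parameter table in Appendix I lists the tests and their timing, also without ranges.

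**Liver tests.** Section 3.1.7 requires "Adequate renal and hepatic function within 14 calendar days prior to registration, defined as follows". Its sub-items include total bilirubin below 2 x ULN (3.1.7.2) and AST or ALT at or below 3 x ULN (3.1.7.3). Checklist item 13 requires adequate hepatic function under Section 3.1, and Appendix I lists bilirubin and AST/ALT at 14 days before registration. Section 3.2.13.6, which excludes hepatic insufficiency with jaundice or coagulation defects, adds that "laboratory tests for liver function and coagulation parameters are not required for entry into this protocol".

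**The concern.** An entry range needs both bounds to hold at once. Joined by *or*, the two bounds form a condition that every value meets. All five lines share the wording, and no other part of the protocol states the ranges, so a site, auditor or eligibility reviewer has no correct version to fall back on.

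The tests bear on harms that the protocol itself anticipates. Section 7.3.5 lists low magnesium, potassium and calcium among expected cisplatin events, and Section 7.4.6.2 describes hepatobiliary events with lapatinib. Eligibility status also decides who enters the sensitivity analyses described in 13.6.3 and 13.6.4. Sites or reviewers who read the criteria differently would classify the same patient differently.

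On the liver side, a site cannot treat the tests both as required (3.1.7) and as not required (3.2.13.6). The conjunction in 3.1.7.3 leaves open what happens when one enzyme is within the limit and the other is not.

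**Working it through.** The plan gives no figure to reproduce here. The check is one of logic and of comparing the text.

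**1. Electrolytes and glucose.** Let L be the lower bound and U the upper bound. As written, a value x is accepted if x > L *or* x < U. To be rejected, x would have to satisfy x ≤ L *and* x ≥ U, which is impossible when L < U.

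| Analyte | L | U | L < U | Rejected as written | Rejected with *and* |
|---|---|---|---|---|---|
| Magnesium (mg/dl) | 0.9 | 3 | yes | none | ≤ 0.9 or ≥ 3 |
| Calcium (mg/dl) | 7 | 12.5 | yes | none | ≤ 7 or ≥ 12.5 |
| Glucose (mg/dl) | 40 | 250 | yes | none | ≤ 40 or ≥ 250 |
| Potassium (mmol/L) | 3 | 6 | yes | none | ≤ 3 or ≥ 6 |
| Sodium (mmol/L) | 130 | 155 | yes | none | ≤ 130 or ≥ 155 |

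Examples: potassium 2.0 passes because it is below 6, and 7.5 passes because it is above 3. Magnesium 0.3 passes because it is below 3, and 8 passes because it is above 0.9. A numerical check over 200,001 values per analyte, running well past both bounds, found no rejected value for any of the five.

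**2. Do the other laboratory limits still work?** Yes.
- ANC, platelets and hemoglobin (3.1.6) each have a single lower bound.
- Total bilirubin (3.1.7.2) has a single upper bound.
- The renal rule (3.1.7.1) also uses *or*, but between two different measures: creatinine < 1.5 mg/dl or clearance ≥ 50 ml/min. A patient with creatinine 1.6 and clearance 40 meets neither and is excluded.

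**3. The transaminase limit (3.1.7.3).** Read literally, the line is met if either enzyme is ≤ 3 x ULN.
- AST 4 x, ALT 4 x: excluded, so the rule is not empty.
- AST 2 x, ALT 10 x: admitted on the literal reading, excluded if both enzymes must comply.

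The second case shows why the reading matters. An ALT of 10 x ULN is already above the 8 x ULN level at which Section 7.7.4.2 calls for interruption on treatment.

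**4. Are liver tests needed for entry?** Section 3.1.7, checklist item 13 and Appendix I say yes. The note in 3.2.13.6 says no.

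**5. Statistical reach.** Sections 13.6.3 and 13.6.4 include all randomized patients in the main analyses. Eligible patients with on-study and follow-up data form a sensitivity analysis only. The 69 events, the 142 patients and the one-sided 0.20 level do not depend on the electrolyte limits.

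**The case against.** **The intended meaning is obvious.** The limits are called required, and item 14 asks for results *within* them, which implies a window. Section 3.0 gives sites a contact for eligibility questions. This stands: many sites will have read the lines as ranges, and nothing in the documents shows otherwise. It lowers the practical weight but does not correct the rule.

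**Entry limits are not the only protection.** Appendix I schedules the electrolytes and glucose every 7 days during treatment. Section 7.2.1.2 requires hydration and correction of pre-existing dehydration around cisplatin. Section 11.2.5 repeats the liver tests at 4 weeks, and 7.7.4 has liver stopping and interruption rules. This stands too, and it limits the safety argument.

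**The liver conflict has a benign reading.** Three places require the tests and one does not. The note in 3.2.13.6 may mean only that this particular exclusion adds no further testing. Likewise, 3.1.7.3 may simply let a site use whichever enzyme it measures. Both readings are reasonable, so the first is a textual conflict to reconcile and the second an ambiguity rather than a demonstrated error.

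**A change comes late.** Section 13.5 projects the end of accrual around March 2017, and Section 7.9 carries the date 3/22/17. A prospective amendment may reach few or no patients. This stands. The remaining value lies mainly in eligibility review and the eligible-patient sensitivity analysis.

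**Stronger readings to avoid.** A reader might infer that the whole laboratory screen fails. It does not, since the limits in 3.1.6, 3.1.7.1 and 3.1.7.2 exclude patients as written. A reader might also infer that patients with dangerous values were enrolled. The documents give no data on that and no basis for estimating it.

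**Conclusion.** The point holds as a drafting error of minor to moderate weight. All five electrolyte and glucose limits are empty as written, and no other passage supplies the ranges. That conclusion needs no assumption beyond a literal reading and L < U, which is true of each line. It describes the rule, not the patients enrolled under it.

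The conflict over whether liver tests are required for entry is real but narrow, with the weight of the text on the side of requiring them. The one-or-both-enzymes question in 3.1.7.3 needs clarifying.

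It would be tempting to extend this to the trial's statistical conclusions. The documents do not support that: the main analyses are by intention to treat, and no design figure changes. The only analysis touched is the sensitivity analysis restricted to eligible patients, and its size cannot be judged without laboratory data.

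**What to change.** 1. In 3.1.8.1 to 3.1.8.5, replace *or* with *and*, leaving the protocol's own bounds unchanged. The tests are already required, so this adds none.
2. Apply the same range reading when eligibility is determined for the sensitivity analyses in 13.6.3 and 13.6.4, and record that decision before the treatment comparison is seen. Values already collected within 14 days of registration are enough.
3. Reconcile the note in 3.2.13.6 with 3.1.7, checklist item 13 and Appendix I, so that the protocol says one thing about liver tests at entry.
4. Have the sponsor state whether 3.1.7.3 applies to one enzyme or both when both are measured.

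The cost is a wording amendment and a short note to whoever reviews eligibility. An extra test could arise only if the sponsor decides that both enzymes must be measured, and then only at sites that measure one. If accrual has already closed, items 1, 3 and 4 can be handled as a documented clarification used in eligibility review.

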3.2 Conditions for Patient Ineligibility (9/27/16)

- 3.2.1 Patients with T1 any N or with T2 N1 are ineligible except for specific oropharynx or hypopharynx patients as described in Section 3.1.3;
- 3.2.2 Patients with simultaneous primaries or bilateral tumors;
- 3.2.3 Gross total excision (e.g., by tonsillectomy) of the primary tumor; however, partial removal of the tumor to alleviate an impending airway obstruction does not make the patient ineligible.
- 3.2.4 Prior invasive malignancy (except non-melanomatous skin cancer) unless disease free for a minimum of 3 years; noninvasive cancers (for example, carcinoma in situ of the breast, oral cavity, or cervix are all permissible) are permitted even if diagnosed and treated < 3 years ago;
- 3.2.5 Prior systemic chemotherapy for the study cancer; note that prior chemotherapy for a different cancer is allowable;
- 3.2.6 Prior radiotherapy to the region of the study cancer that would result in overlap of radiation therapy fields;
- 3.2.7 Primary site of tumor of oral cavity, nasopharynx, sinuses, or salivary glands;
- 3.2.8 Initial surgical treatment, excluding diagnostic biopsy of the primary site or nodal sampling of neck disease; radical or modified neck dissection is not permitted.
- 3.2.9 Prior allergic reaction to the study drugs;
- 3.2.10 Prior therapy that specifically and directly targets the EGFR/HER2 pathway;
- 3.2.11 Patients who have current active hepatic or biliary disease (with exception of patients with Gilbert's syndrome, asymptomatic gallstones, or stable chronic liver disease per investigator assessment);
- 3.2.12 Pregnant women or women of childbearing potential and men who are sexually active and not willing or able to use medically acceptable forms of contraception; this exclusion is necessary because the treatment involved in this study may be significantly teratogenic.
- 3.2.13 Severe, active co-morbidity, defined as follows:

- 3.2.13.1 Uncontrolled cardiac disease, such as uncontrolled hypertension or unstable angina;
- 3.2.13.2 Transmural myocardial infarction within the last 6 months;
- 3.2.13.3 History of congestive heart failure and/or history of left ventricular ejection fraction < 50%;
- 3.2.13.4 Acute bacterial or fungal infection requiring intravenous antibiotics at the time of registration;
- 3.2.13.5 Chronic Obstructive Pulmonary Disease exacerbation or other respiratory illness requiring hospitalization or precluding study therapy within 30 calendar days prior to registration;
- 3.2.13.6 Hepatic insufficiency resulting in clinical jaundice and/or coagulation defects; note, however, that laboratory tests for liver function and coagulation parameters are not required for entry into this protocol.
- 3.2.13.7 Acquired Immune Deficiency Syndrome (AIDS) based upon current CDC definition; note, however, that HIV testing is not required for entry into this protocol. The need to exclude patients with AIDS from this protocol is necessary because the treatments involved in this protocol may be significantly immunosuppressive. Protocol-specific requirements may also exclude immuno-compromised patients.

4.0 PRETREATMENT EVALUATIONS/MANAGEMENT

NOTE: This section lists baseline evaluations needed before the initiation of protocol treatment that do not affect eligibility.

4.1 Required Evaluations/Management

- 4.1.1 If the patient consents to participate in the quality of life (QOL) component of the study, sites are required to administer the baseline QOL and PRO assessments prior to the start of protocol treatment: the PSS-HN, FACT-HN, and XeQOLS.

4.2 Highly Recommended Evaluations/Management

The following pre-treatment evaluations/interventions are not required but are highly recommended.

- 4.2.1 Dental evaluation and if applicable, prophylaxis, within 84 calendar days prior to the start of treatment (see Appendix VII, Dental Management);
- 4.2.2 Whole body PET/CT scan within 42 calendar days prior to the start of treatment;
- 4.2.3 Baseline audiogram within 84 calendar days prior to the start of treatment;
- 4.2.4 Assessment of swallowing (dysphagia) within 28 calendar days prior to the start of treatment;
- 4.2.5 Nutritional evaluation for a prophylactic gastrostomy (PEG) tube placement any time prior to the start of treatment; **note:** In RTOG 99-14, a completed phase II trial assessing the feasibility of combining accelerated fractionation by concomitant boost with cisplatin, 79% of patients who did not have prophylactic PEG placement prior to treatment required placement of PEG during treatment

5.0 REGISTRATION PROCEDURES (8/13/15)

Note: This is a limited institution study; see participating institutions on the RTOG web site.

IGRT is mandatory when using reduced PTV margins (<5 mm). If the institution is not head and neck IGRT credentialed, contact the ACR Core Laboratory/RTQA Credentialing at [contact].

5.1 Regulatory Pre-Registration Requirements (10/3/13)

- 5.1.1 Prior to the recruitment of a patient for this study, investigators at participating institutions must maintain an "active" investigator registration status through the annual submission of a complete investigator registration packet (FDA Form 1572 with original signature, current CV, Supplemental Investigator Data Form with signature, and Financial Disclosure Form with original signature) to the Pharmaceutical Management Branch, CTEP, DCTD, NCI.

Each investigator or group of investigators at a participating site must obtain IRB approval for this protocol and submit IRB approval and supporting documentation to the RTOG Headquarters ([contact]) or e-mail them to [contact]. The following study-related regulatory documentation is required:

- Institutional Qualifying Questionnaire with RTOG approval for participation;
- RT Credentialing for IMRT and IGRT;
- IRB/REB initial approval letter;

- IRB/REB approved consent (English and native language versions*); *Note: Institutions with a large number of patients whose primary language is not English must provide certification/verification of IRB/REB consent translation to RTOG Headquarters (described below in Section 5.1.1.1);
- IRB/REB assurance number including renewal information, as appropriate;
- Study Agent Shipment Form (SASF) [available on the RTOG web site, www.rtog.org, under protocol-specific materials/regulatory resources];
- All subsequent amendment and annual approvals;
- All Regulatory submissions must also include a completed IRB certification Form as a cover sheet.

Note: In the event of an amendment of this protocol, sites should submit their amended consent form to RTOG Regulatory for approval **prior** to IRB/REB submission. Sites can submit the consent form with tracked changes to [contact].

5.1.1.1 Translation of documents is critical. The institution is responsible for all translation costs. All regulatory documents, including the IRB/REB approved consent, must be provided in English and in the native language. Certification of the translation is optimal but due to the prohibitive costs involved RTOG will accept, at a minimum, a verified translation. A verified translation consists of the actual REB approved consent document in English and in the native language, along with a cover letter on organizational/letterhead stationery that includes the professional title, credentials, and signature of the translator as well as signed documentation of the review and verification of the translation by a neutral third party. The professional title and credentials of the neutral third party translator must be specified as well.

5.1.2 Pre-Registration Requirements for the Initial Shipment of Lapatinib:

5.1.2.1 Participating Institutions:

All pre-registration requirements must be met before registering the first case. Institutions must electronically complete (versus hand write) a Study Agent Shipment Form (SASF), which is available on the RTOG web site, www.rtog.org, under protocol-specific materials/regulatory resources. Institutions must submit the SASF to RTOG Headquarters by [contact] or e-mail: [contact] as soon as the individual responsible for the study agent has been identified.

5.2 Pre-Registration Requirement: Central Pathology Review

Central pathology review for eligibility is required prior to registration. Pathology materials and a pathology report must be submitted to the Central Pathology Reviewer. (See Section 10.2.)

5.3 Registration (9/27/16)

5.3.1 Summary of Procedures

This study incorporates a two-step registration process for oropharyngeal patients.

5.3.1.1 All patients can be registered after completing the Eligibility Checklist, Step 1 via online registration.

All patients, except patients with oropharyngeal cancer, then can be randomized after completing the Eligibility Checklist, Step 2 via online registration.

See Section 5.3.2 online for registration instructions.

5.3.1.2 Oropharyngeal carcinoma patients must consent to submit tissue for HPV analysis; see Section 10.2 for details of submission. The Biospecimen Bank at UCSF will process 4 unstained slides from the tissue block submitted and will send the slides to [name] for HPV analysis. The results of the HPV analysis are expected in approximately 7-10 business days, and RTOG Headquarters will inform sites by e-mail of the completion of the HPV analysis. At this point, oropharyngeal carcinoma patients may be randomized; sites must complete the Eligibility Checklist, Step 2 via online registration.

Note: If a specimen was previously submitted to the Biospecimen Bank at UCSF for determination of HPV status for another RTOG trial and found to be p16 negative, investigators can forward a Specimen Transmittal (ST) Form to the Biospecimen Bank at UCSF requesting that the specimen be sent to [name] for central lab confirmation of p16 negativity.

